historical treatments across mood and psychotic disorders. It allows extraction of other historical measures for antidepressants: ATRQ (Fava and Davidson, 1996; Fava, 2003); for lithium: the Alda Scale (Grof JCP 2002): The questionnaire captures treatment duration, response, and reason for discontinuation. In the present study, FAST is a means of recording number and type of prior antipsychotic trials, to define treatment resistance for purposes of stratification.

SAFER Rater Assessment

In order to confirm diagnosis and to ensure patients are appropriate for the study, remote diagnostic assessments (SCID-I/P Psychosis module), and disease severity assessments (PANSS, MGH FAST, and CGI-S) will be performed remotely by an independent MGH CTNI rater. The subject will be provide contact information and a SAFER interview will be scheduled within 27 days of Visit 1 (screening). Sites will be notified of the results within 24 hours of the interview.

Efficacy Measures

The Positive and Negative Syndrome Scale (PANSS) (Kay, 1987) will be used to measure symptom severity in this trial. PANSS is a 30-item questionnaire used to evaluate schizophrenia symptoms, based on the clinical interview as well as reports of family members or primary care hospital workers. PANSS consists of Positive scale (7 items), Negative scale (7 items), and General Psychopathological scale (16 items) sections. Each item (symptom) will be scored on a 7-point scale with higher scores representing increasing levels of psychopathology: 1) Absent, 2) Minimal, 3) Mild, 4) Moderate, 5) Moderate severe, 6) Severe, and 7) Extreme.

Each of the 30 items is accompanied by a specific definition as well as detailed anchoring criteria for all seven rating points. Ratings will be performed by the Investigator or qualified sub-Investigator. The highest applicable rating point is always assigned, even if the subject meets criteria for lower points as well. In judging the level of severity, the rater must utilize a holistic perspective in deciding which anchoring point best characterizes the subject's functioning and rate accordingly, whether or not all elements of the description are observed. The determined results must be documented on the source documents and in the CRF.

For the purpose of this study, the total PANSS score along with sub-scores for Positive scale, Negative scale, General Psychopathology scale, and Composite scale will be derived as follows:

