A 10-minute run-in period ("Phase I") has been added to ensure that the patient tolerates the drug. As determined by consulting cardiologist, this will include the administration of the drug at half of the rate (0.25 mcg/kg/min). The following Safety parameters will be followed for Phase I:

Safety Parameters

Safety Parameters Phase I dose:

- If SBP \leq 89 STOP infusion. Lie flat, feet up, call N.P. & P.I.
- If HR $>$ 120 bpm or $>$ 20 bpm over baseline HR, abort study
- If SpO2 $<$ 92%, stop infusion
- If patient reports headache, ask: "do you feel this headache is tolerable?"
 - If patient says "yes," continue dose
 - If patient says "no," STOP dose

-If patient experiences symptomatic hypotension (nausea, dizziness) STOP infusion.

If Phase I is tolerated per the above guidelines after the 10 minute run-in period, the drug will be administered at the rate of 0.5 mcg/kg/min ("Phase II") with the following parameters:

Safety Parameters for Phase II dose:

- If SBP between 81 and 89, lower dose to Phase I dose for 15 min. Monitor with CRC NP.
- If SBP rises to > 89mm Hg continue Phase I dose
- If SBP remains between 81 and 89mm Hg abort and call P.I.
- If SBP < 80, STOP infusion, lie flat, feet up & call P.I.
- If HR > 120 bpm or > 20 bpm over baseline HR, lower dose to Phase I dose for 15 min
- If SpO2 < 92% Stop infusion
- If patient reports headache, ask, "Do you feel this headache is tolerable?"
 - If patient says "yes", continue dose
 - If patient says "no", *lower dose to Phase I dose for 15 min*
- If better, continue Phase I dose
- If still intolerable, STOP dose
- If patient experiences symptomatic hypotension (nausea, dizziness) *lower dose to Phase I dose for 15 min*
- If better, continue Phase I dose
- *If not, Stop infusion, call P.I.*

Should the patient require PRN rescue medications, the following procedures will take place:

PRN Rescue medications:

In consultation with CRC N.P.

For SBP < 80 mmHg, may give 250 ml 0.9% NS

IV bolus via Sigma pump @999 ml/hr over 15 min X 2

For rash may give

Diphenhydramine 25 mg by mouth X 1

The IV line will be left in place for at least 1 hour following the infusion to allow for additional medications to control emergent side effects. If additional IV medication is necessary, an anesthesiologist, cardiologist, or medically qualified designate will start the infusion and a medical team will be present during the entire infusion period.

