A study psychiatrist or medically qualified designate will release the subject at the conclusion of the testing period at the end of the visit. A trained research assistant along with a research nurse will be present during the entire infusion and monitoring period. The psychiatry research staff member will administer rating scales. All side effects and vital parameters will be recorded during the infusion and 2 hours following. Any abnormal, clinically significant vital signs will be recorded as adverse events.

Discharge Procedure: Gross motor and cognitive function, ataxia, reflexes/clonus will be evaluated and documented by a study psychiatrist or medically qualified designate prior

to discharge. Before being discharged patients should be awake and alert, feeling well, with no nausea, vertigo, or dizziness. There should be no significant change in vital signs from prior to infusion. They will be given a small meal before discharge.

Patients will be instructed not to drive. If necessary, the study nurse will release them to the care of an adult family member or caregiver, who will accompany the patient home.

Reliability Training

All physicians/raters involved in the assessment of study subjects will use standardized clinician-rated measures such as the SCID I/P, the PANSS, and CGI-S. Training in the use of these instruments occurs through videotaped and live interviews of mock patients. Both intra-individual and inter-individual reliability measures will be reported.

Patient Adherence to Protocol

Every effort will be made to encourage patients to comply with the procedures and the assessments involved in study. Patients will be compensated for their time at each visit, at a rate determined appropriate by each individual IRB (estimated compensation: \$20.00/hour). This level of subject compensation, while non-coercive, facilitates adherence to assessments and procedures that require weekly visits.

Subjects and clinicians will be asked to guess which arm of the study the subjects were in at the end of the study to assess if blinding was successful.

Evaluation of Adverse Events (AEs)

Definition

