Subjects will receive either sodium nitroprusside diluted with 5% dextrose and infused at a rate 0.5 µg/kg/min for 4 hours, or a placebo solution of 5% dextrose infused over 4 hours. The study treatment will not be exposed to light prior to and during the infusion as exposure of SNP to light has the potential to form cyanide ions. Subjects will be recumbent and blood pressure, heart rate, blood oxygen saturation, and ECG will be continuously monitored during infusion of the study treatment.

Study Product Supplies and Administration

The Institutional Pharmacy will issue either undiluted sodium nitroprusside in sterile 5% dextrose or sterile 5% dextrose only. For subjects randomized to sodium nitroprusside, an unblinded pharmacist will dilute the SNP with 5% dextrose to achieve a concentration allowing infusion of 0.5 µg/kg/min over the course of 4 hours.

Packaging and Labeling

Sodium nitroprusside or placebo will be prepared within 12 hours from the scheduled delivery time and once prepared in solution will be protected from UV light by covering the iv bag with an aluminum foil bag. The intravenous drip chamber will also be covered for blinding purposes but the tubing does not need to be covered.

A study label that includes the subject ID and randomization ID will be pasted to the foil bag so that it is clearly visible. The dextrose solution will also be covered with an identical foil bag and study label so that medical personal administering the i.v. will be blinded to the study treatment.

Dose Modification during Treatment

As previously stated, the subject's blood pressure will be monitored continuously during the study treatment. If the subject's systolic blood pressure falls below 90 mm Hg the

infusion rate will be reduced by 50% and a drop below 80 mm Hg will terminate the infusion. Nitroprusside has a circulating half-life of 2 minutes and blood pressure is usually restored within 1-5 minutes of stopping the infusion. Trendelenburg position and IV fluids will be used if subjects experience symptomatic hypotension. The medical monitor will receive all safety data within 24 hours after each infusion and will inform the PI who will inform the IRB of any safety concerns.

Possible Drug Interactions

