Treatment (infusion) discontinuation will be determined by the criteria outlined in the Infusion Monitoring and Discharge Procedures section of this Protocol. A study physician will be available for consultation on any participant safety issues that arise during the infusion.

A patient who decides to discontinue participation in the study will always be asked about the reason(s) and the presence of any AEs. If possible, they will be seen and assessed by an investigator. AEs will be followed up until resolution.

Procedures for Discontinuation from Study:

If a patient discontinues from the study before randomization, then no further follow-up will be expected. However, if the patient discontinues after randomization, but before receiving any study treatment, the patient will be asked to return for a final study visit, during which the procedures outlined in the Visit 9 Final Visit/Early Termination Visit procedures will be completed, including AEs and concomitant medication assessments.

If a patient discontinues from the study before completion and has received the dose of study drug, the patient will be asked to return for a final study visit, at which the procedures outlined in the Early Termination Visit will be completed. Every effort should be made to follow up with patients who discontinue from the study prior to Visit 9 (Day 28). If patients refuse to return to the clinic for the study-related assessments, a modified follow-up through, for example, regular telephone contact or a contact at study closure should be arranged, if agreed to by the patient and in compliance with local data privacy laws/practices. If the patient refuses follow-up, the reason for the refusal and last contact date should be documented in the eCRF and source documents.

Patients who discontinue from the study will not be replaced.

If an Early Termination Visit is warranted, the following procedures will be performed:

- Concomitant medications
- Vital Signs
- 12-lead ECG
- Anthropometrics (weight, height, waist circumference, BMI)
- CBC with differential and Comprehensive Metabolic Panel (CMP)
- Urinalysis
- Serum Pregnancy test
- PANSS
- CGI-S

- CGI-I
- AE/SAE assessment
- AIMS
- SAFTEE
- C-SSRS
- MATRICS
- UPSA-B

Unblinding Procedure

Methods for Ensuring Blinding

The investigator, subject, and study staff will be blinded. The preparation and labeling of the study drugs will be performed by the site pharmacy in a way to ensure blinding throughout the study.

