No members of the study team at study sites, will have access to the randomization scheme during the conduct of the study, with the exception of the Site's unblinded pharmacist or nurse as designated by the PI.

The randomization schedule for blinding of randomized treatment will be maintained by MGH CTNI or representative and will not be disclosed until after database lock.

During the infusion visits, the study staff conducting the clinical efficacy assessments must not be able to view the bag containing the infusion solution to ensure that they remain blinded. The bag must be protected from view with an opaque covering.

Methods for Unblinding the Study

Individual treatment codes, indicating the treatment randomization for each randomized patient, will be available to the investigator(s) or pharmacists from MGH CTNI or its designee.

The treatment code must not be broken except in medical emergencies when the appropriate management of the patient necessitates knowledge of the treatment randomization. The investigator documents and reports the action to MGH CTNI or representative, without revealing the treatment given to the patient to MGH CTNI or representative's staff.

MGH CTNI retains the right to break the code for serious adverse events (SAEs) that are unexpected and are suspected to be causally related to a study drug and that potentially require expedited reporting to regulatory authorities. Treatment codes will not be broken

for the planned analyses of data until all decisions on the evaluability of the data from each individual patient have been made and documented.

J. ETHICAL CONSIDERATIONS

Risk/Benefit Assessment

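### Rater blinding hides the infusion apparatus but not infusion-day vital signs, rate changes or adverse events, and the Protocol gives two answers on who rates the PANSS

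*Protocol*

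**What the plan says.** The blind rests on concealing the equipment. Under Methods for Ensuring Blinding (Protocol section I), efficacy raters on infusion visits "must not be able to view the bag containing the infusion solution". Packaging and Labeling gives placebo an identical foil bag and label and adds: "The intravenous drip chamber will also be covered for blinding purposes but the tubing does not need to be covered". The general statement is "The investigator, subject, and study staff will be blinded". No site team member has access to the randomization scheme, "with the exception of the Site's unblinded pharmacist or nurse as designated by the PI".

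Two places in section H say who rates:
- Efficacy Measures, on the PANSS: "Ratings will be performed by the Investigator or qualified sub-Investigator".
- Infusion Monitoring and Discharge Procedures: "The psychiatry research staff member will administer rating scales".

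The latter section also sets the safety responses. Pressure, heart rate and oxygen saturation are recorded every 5 minutes for 30 minutes and then every 10 minutes. Listed triggers lower or stop the infusion, and several involve the P.I., for example: "If SBP < 80, STOP infusion, lie flat, feet up & call P.I". Under Performing Adverse Events Assessments, the PI or a delegated medically qualified Sub-Investigator judges whether each event is drug-related.

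The only check of the blind is under Patient Adherence to Protocol: "Subjects and clinicians will be asked to guess which arm of the study the subjects were in at the end of the study".

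**The concern.** Sodium nitroprusside is a vasodilator, and the Protocol itself lists low pressure, raised heart rate, headache, nausea and dizziness as things to watch for. A covered bag hides none of these, nor a rate cut. The PANSS total is a clinician's judgement and the sole primary endpoint. A rater who has seen or been told of such a cue may form a belief about treatment and carry it into later scores.

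Both SPCD stages are exposed, since each begins with an infusion. The Study Design section also classifies response from the Visit 4 and Visit 7 PANSS, both infusion days, so ratings on those days help decide who enters the Stage 2 comparison. If the blind were compromised, the one planned check would be hard to interpret.

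**Working it through.** **1. What is kept from the rater.**

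| Information | Safeguard in the documents |
|---|---|
| Bag contents | Opaque cover, identical foil bag and label |
| Drip chamber | Covered |
| Treatment code | Withheld from site staff other than the designated unblinded pharmacist or nurse |
| Vital signs and monitor | None stated |
| Infusion rate, reductions, stops | None stated |
| Adverse events during infusion | None stated |

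**2. Whether rater and safety roles can coincide.** Under Efficacy Measures the rater is the Investigator or a sub-Investigator. The P.I. is called for low pressure in the half-rate run-in, and at the full rate for pressure below 80, pressure that stays at 81 to 89, or symptomatic hypotension that does not improve. Dose Modification during Treatment also has the medical monitor inform the PI after receiving each infusion's safety data. The PI or a Sub-Investigator judges relatedness. Under Infusion Monitoring the rater is instead a psychiatry research staff member, but no sentence bars that person from the safety data. So the overlap is permitted, not certain.

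**3. When the infusion-day PANSS is rated.** The Synopsis places it at Hour 3 to 4, while the infusion is running. The visit schedule places it between hours 4 and 7, in the same list as vital signs and adverse events. Either way the cues come first.

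**4. The plan's own power.** Inputs from Sample Size Determination: differences 9 and 11, weight 0.5, SD 14, 20% attrition, 30% placebo response; 20 active and 40 placebo subjects in Stage 1.
- Stage 2 per arm: 20 × 0.80 × 0.70 = 11.2 (the plan gives about 11).
- V1 = 14² × (1/20 + 1/40) = 14.7; V2 = 14² × (2/11.2) = 35.0.
- SE = √[0.25 × (14.7 + 35.0)] = 3.52 points.
- Power = Φ(10/3.52 − 1.96) = 0.810, against the stated 81%. It reproduces.
- Smallest significant weighted difference: 1.96 × 3.52 ≈ 6.9 points.

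**5. Illustration of size.** Assume no true effect. In each stage a fraction f of active subjects is recognised and rated b points better at the outcome visit, with baseline unaffected and SD unchanged. The bias is f × b, and the two-sided rejection rate is Φ(fb/SE − 1.96) + Φ(−fb/SE − 1.96).

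| f | b | Bias (points) | Type I error |
|---|---|---|---|
| 10% | 5 | 0.5 | 0.052 |
| 20% | 5 | 1.0 | 0.059 |
| 30% | 5 | 1.5 | 0.071 |
| 20% | 10 | 2.0 | 0.088 |
| 50% | 5 | 2.5 | 0.109 |
| 50% | 10 | 5.0 | 0.294 |

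The documents give neither f nor b.

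**6. What 0 of 10 shows.** The Protocol cites no adverse effects, including no hypotension, in 10 treated subjects of the earlier pilot trial. The exact two-sided 95% upper limit is 1 − 0.025^(1/10) = 31%.

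**7. The guess.** It comes after both infusions and all efficacy ratings, so a correct answer may reflect perceived benefit as well as side effects. It is asked of clinicians, not specifically of the PANSS rater. Neither Protocol section M nor the SAP plans an analysis of it.

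**The case against.** The other side has real substance. The masking goes beyond the bag: the drip chamber is covered, placebo has an identical foil bag and label, and both arms receive a 4-hour infusion. Pressure monitoring belongs to a cardiologist, anesthesiologist or designate with one-to-one nursing, and one sentence gives the scales to psychiatry research staff. Placebo subjects can also meet the triggers, so a call to the P.I. is a cue and not a disclosure. Few cues are expected: the pilot reported none in 10 treated subjects, two of them on chlorpromazine, and this trial excludes chlorpromazine and symptomatic orthostatic hypotension and starts with a half-rate run-in.

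These points limit the finding. A reader might infer that the P.I. will rate the PANSS and be unblinded; the documents only leave that possible. A reader might also infer bias toward the drug in both stages. The direction is not settled, because Study Design calls Visit 4 the baseline for response, and the only Visit 4 PANSS comes during or after the infusion. If that score served as baseline, a favourable same-day rating would lower it and work against the drug. Visit 3, however, is also labelled Phase 1 Baseline.

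Nor is the guess useless. It could show better-than-chance guessing, and if arm means sequence, each answer implies a guess for each stage; the question's wording is not given.

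What the objection does not supply is any sentence separating raters from safety information. Zero events in 10 is compatible with a rate up to 31%, and headache or a faster pulse can serve as a cue without hypotension.

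**Conclusion.** The gap is real. Rater blinding covers the infusion apparatus only, the Protocol disagrees with itself on who rates, and one of its two versions lets the same person rate the PANSS, take the hypotension call and judge relatedness.

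This is a risk of bias, not demonstrated bias. Its size is unknown: the illustrative type I error of about 0.052 to 0.294 depends wholly on assumed f and b, and on all bias running toward the drug with baseline unaffected. A single figure, such as 1.5 points or 15% of the 10-point target, would rest on invented inputs and should not be read as an estimate. The sample size calculation is unaffected.

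The change is worth making because the endpoint is subjective and the only primary one, and the remedy is cheap.

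**What to change.** 1. Reconcile Efficacy Measures with Infusion Monitoring and Discharge Procedures on who rates the PANSS.
2. Extend Methods for Ensuring Blinding. For a given subject, the PANSS rater has no access to that subject's infusion-day vital signs, monitor, infusion rate or adverse event record. The rater is also not the clinician called under the safety parameters, nor the one judging that subject's infusion adverse events. Draw on staff already described under Infusion Monitoring, and leave every safety response as it stands.
3. Have the PANSS rater give the existing end-of-study guess separately for each infusion, with the reason, and state in the SAP that it will be reported by stage.

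The cost is less flexibility in who rates at each site. Subjects may still mention headache or dizziness to the rater, so the protection is partial. Asking for guesses at Visits 4 and 7 would reduce confounding with later perceived benefit, but it may prompt treatment beliefs before later ratings. That is a debatable trade-off and not part of this recommendation.

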APPENDIX 1: SCHEDULE OF EVENTS

SNP Study Schedule of Events	OPD	CTNI Interview	OPD	Monitoring Unit Double-Blind Treatment Phase 1		OPD	OPD	Monitoring Unit Double-Blind Treatment Phase 2		OPD			
				Screen	Remote	Baseline	iv SNP -0.5 µg/kg/min or iv 5% glucose	iv SNP -0.5 µg/kg/min or iv 5% glucose	Final FU or ET				
N= 60 SPCD Design													
Visit	1	2	3	4			5	6	7	8	9		
Day	-28 to -13	-13 to -3	-2 to -1	Day 0**	Hrs 0-4	Hrs 5-7	D7	D12-13	Day 14**	Hrs 0-4	Hrs 5-7	D21	D28
Informed Consent	X												
Subject ID Assignment	X												
SCID-I/P	X												
MGH-FAST	X												
PANSS	X		X			X	X	X		X	X		
CGI-5 / CGI-I	X		X			X	X	X		X	X		
C-SSRS	X		X			X	X	X		X	X		
I/E Criteria	X												
CTNI Rater (PANSS CGI-5 MGH FAST)		X											
Demographics	X												
Physical Exam and Medical History	X												
Vital Signs and 12-Lead ECG	X		X	X		X	X	X		X	X		
Anthropometrics (ht wt waist circumference)	X		X	X		X	X	X		X	X		
Psychiatric History	X												
HbA1c	X												
CBC and CMP	X			X					X		X		
Urinalysis	X			X				X					
Urine Drug Screen	X			X				X					
Serum Pregnancy Testing	X												
Blood sample for DNA	X												
AE/SAE Assessment	X		X		X	X	X	X	X	X	X		
Conmed Assessment	X		X	X		X	X	X		X	X		
AIMS			X			X	X*	X		X	X*		
SAFTEE			X			X	X*	X		X	X*		
MATRICS			X			X	X*	X		X	X*		
UPSA-B			X			X	X*	X		X	X*		
Randomization ID (allocation ratio 1:1:1)		X							X				
Pre-infusion neurological exam				X					X				
Cardio-pulmonary monitoring					X				X				
iv Na nitroprusside or Placebo						X			X				
Post-infusion neurological exam							X			X			
Post-infusion De Brief							X			X			

X* - discontinued as of 10/2015

** +/- 1 day with permission from CTNI

